10.3 Safety Assessments

10.3.1 Adverse Events

Adverse events will be assessed and reported at each visit. Adverse events will be graded according to the NCI-CTCAE version 4.03 ([NCI-CTCAE v4.03, 2010](#)).

Details on AEs monitoring and reporting are provided in Section 11.

10.3.2 Vital Signs

Vital signs including temperature, blood pressure and heart rate should be recorded at each visit. Within each visit, preferably the same equipment shall be used for vital signs measurements. Vital signs should be assessed just before and no longer than 30 minutes before infusion start, and within 30 minutes after the infusions.

10.3.3 Electrocardiograms

Single 12-lead ECG will be obtained as outlined in the Schedule of Activities ([Table 1](#)) using a local ECG machine that automatically calculates the heart rate and measures PR, QRS, QT, and QTc intervals. ECG results will not be recorded in the eCRF except for clinically significant results that must be reported as an AE.

10.3.4 Clinical Safety Laboratory Assessments

Laboratory tests should be collected as outlined in the Schedule of Activities ([Table 1](#)) and assessed in accordance with local standards. Screening laboratory samples do not need to be repeated if these were performed as part of the base trial within 21 days before Cycle 1 Day 1 of the current trial. Laboratory results will not be recorded in the eCRF except for clinically significant results that must be reported as an AE. If a laboratory result is deemed to be an AE, this should be reported in the eCRF including the laboratory value and the relevant reference range. Retesting is required only if clinical symptoms appear.

A blood sample for pregnancy test will be drawn at the Screening Visit and at the start of each treatment cycle from all women of childbearing potential.

The following safety laboratory tests should be collected:

Hematology

Erythrocytes, hemoglobin, hematocrit, leukocytes, neutrophils, lymphocytes, monocytes, eosinophils, basophils, neutrophils (absolute), lymphocytes (absolute), monocytes (absolute), eosinophils (absolute), basophils (absolute) and reticulocytes.

Coagulation

Prothrombin time (INR), aPTT and prothrombin time (sec).

Biochemistry

Sodium, potassium, calcium, magnesium, albumin, glucose, creatinine, creatinine clearance (Cockcroft-Gault), uric acid, blood urea nitrogen, aspartate aminotransferase, alanine aminotransferase, alkaline phosphatase, bilirubin (total), lactate dehydrogenase, creatinine kinase and C-reactive protein.

Serology (only at screening)

Hepatitis B surface antigen, anti-hepatitis B core antigen, anti-hepatitis C virus, cytomegalovirus (CMV) IgG, CMV IgM, human papilloma virus screening, CMV DNA, hepatitis C virus RNA (qualitative).

11. ASSESSMENT AND REPORTING OF ADVERSE EVENTS

11.1 Definitions

11.1.1 Adverse Event

An AE is any untoward medical occurrence in a patient or clinical trial patient, temporally associated with the use of a medicinal product, whether or not considered related to the medicinal product.

NOTE: An AE can therefore be any unfavorable and unintended sign (including an abnormal laboratory finding), symptom, or disease (new or exacerbated) temporally associated with the use of a medicinal product.

11.1.2 Serious Adverse Event

An AE that meets one or more of the following criteria/outcomes is classified as serious (AEs not meeting the below mentioned criteria are classified as non-serious):

- Requires inpatient hospitalization or prolongation of existing hospitalization.
- Results in persistent or significant incapacity or substantial disruption of the ability to conduct normal life functions.
- Is a congenital anomaly/birth defect.
- Medically important.
- Results in death.
- Is life-threatening.

The term “life-threatening” in the definition of “serious” refers to an event in which the patient was at risk of death at the time of the event; it does not refer to an event which hypothetically might have caused death if it were more severe.

Elective surgery overnight for convenience or other scheduled hospitalization periods that were planned before the patient was included in this trial are not to be reported as AEs.

Medical and scientific judgment must be exercised in deciding whether an AE is believed to be “medically important”. Medically important events may not be immediately life-threatening or result in death or hospitalization but may jeopardize the patient or may require intervention to prevent one of the other outcomes listed in the definition above.

11.1.3 Adverse Events of Special Interest

Based on the currently available safety profile for tisotumab vedotin, the below listed events are regarded as adverse events of special interest (AESIs):

- Bleeding-related events
- Neuropathy
- Ocular events (conjunctivitis, ulceration, keratitis, symblepharon)

11.2 Adverse Event Reporting

The investigator must report all directly observed AEs and all AEs reported by the patient. A general type of question should be used similar to “Do you have any health problems?” or “Have you had any health problems since your last visit?”

All AEs must be reported from the time the patient signs the ICF until 30 days after the last dose of tisotumab vedotin, or until the patient withdraws consent or starts subsequent anti-cancer therapy, whichever occurs first.

Any AE (signs, symptoms and diagnosis) occurring prior to signing the ICF must be recorded in the applicable base protocol eCRF.

Registration of Adverse Events in the eCRF:

- All AEs must be recorded in the eCRF.
- Grade 3 and 4 abnormal laboratory test results must be reported as AEs when these are assessed as clinically significant by the reporting investigator.

Reporting of Adverse Events to the Safety CRO:

- All SAEs
- Ocular grade ≥ 2 AEs
- All non-serious grade ≥ 3 AEs
- All events of overdose and/or medication errors, independent of intensity, must be reported as AEs to the Safety CRO.
- Any event of pregnancy must be reported as an AE to the Safety CRO.

Please refer to Section 11.5 for an overview of AE reporting timelines.

All deaths (including deaths due to disease progression) should be reported as an SAE.

11.3 Events Requiring Immediate Reporting

11.3.1 Serious Adverse Events, Non-serious Grade ≥ 3 Adverse Events, Non-serious Grade ≥ 2 Ocular Events, Overdose and/or Medication Errors, and Pregnancies

Serious adverse events, non-serious grade ≥ 3 AEs, non-serious grade ≥ 2 ocular AEs, overdose and/or medication errors, and pregnancies must be reported from the investigational site to the Safety CRO no later than 24 hours following (a) the patient visit at which such AE was reported, noted or recognized; or (b) the principal investigator’s or any investigator personnel’s receipt of the test results or other information at, or from which, such development was reported, noted or recognized.

Completed SAE Report Forms, Non-serious Grade 3 Adverse Event Report Forms, Non-serious Grade 2 Ocular Adverse Event Report Forms or Pregnancy Forms must immediately be forwarded to the Safety CRO [REDACTED].

[REDACTED]

If you have access to a secured email, you may forward completed SAEs, non-serious grade 3 AEs, non-serious grade 2 ocular events forms or pregnancy forms to:

[REDACTED]

If you do not have access to a secured email, please forward completed SAEs, non-serious grade 3 AEs, non-serious grade 2 ocular events forms or pregnancy forms to:

[REDACTED]

11.3.2 Overdose and Medication Errors

An overdose is defined as a patient receiving a dose of the IMP in excess of that specified in this protocol. All cases of overdose must be recorded in the eCRF and reported to the Safety CRO as an AE within 24 hours of knowledge of the event.

Medication errors and uses outside what is foreseen in the protocol, including misuse and abuse of the product, must be recorded in the eCRF and reported to the Safety CRO as an AE within 24 hours of knowledge of the event.

Overdose, medication errors, misuse and abuse do not automatically make an AE serious, but if the consequences are serious, for example death or hospitalizations, the event is serious and must be reported as an SAE (see Section 11.5).

Rescue medication to reverse the action of tisotumab vedotin is not available. In case of overdose, medication errors, misuse and/or abuse of the IMP, patients should receive supportive care according to local guidelines, and potential side effects of tisotumab vedotin should be treated symptomatically.

In the event of an overdose, the investigator should:

- i. Closely monitor the patient for any AE and laboratory abnormalities.
- ii. Contact the Medical Monitor immediately.
- iii. Obtain a plasma sample for PK analysis if requested by the Medical Monitor (determined on a case-by-case basis).
- iv. Document the quantity of the excess dose as well as the duration of the overdose in the eCRF.

11.3.3 Pregnancy

Any pregnancy that occurs during trial participation must be reported. Pregnant trial patients must be withdrawn from treatment immediately, whereas male patients may continue in the trial should pregnancy of female partners occur. In this case, a separate informed consent will be obtained from the female partner for collection of information regarding the pregnancy.

Each pregnancy must be reported to the Safety CRO within 24 hours of learning of its occurrence using the Pregnancy Form. The pregnancy must be followed up to determine outcome (including premature termination) and status of mother and child. The child must be followed at least to the age of one month.

Pregnancy complications and elective terminations for medical reasons must be reported as an AE or SAE. Spontaneous abortions must be reported as an SAE. Any SAE occurring in association with a pregnancy brought to the investigator's attention after the patient has completed the trial and considered by the investigator as possibly related to the IMP must be promptly reported to the Safety CRO.

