8. INVESTIGATIONAL PLAN

8.1 Overall Trial Design and Plan

This is an open-label, multicenter trial to collect long-term safety and efficacy data and to provide ongoing access to tisotumab vedotin for patients with solid tumors who have completed a tisotumab vedotin base trial. Patients demonstrating clinical benefit but who have been withdrawn from the base tisotumab vedotin trials for reasons that are not considered critical and unmanageable for the safety of the patient (as evaluated by the investigator and the sponsor) can also enter this protocol. For patients who received tisotumab vedotin as a single-agent in the base trial, tisotumab vedotin will be given according to the dosing level and schedule administered in the base trial at the time of exiting. Reduced dose can be administered in accordance with the mitigation strategies (Section 9.4 to 9.5.6) or at the discretion of the treating physician based on individual patient observed toxicity profile and after consultation and agreement by the Genmab Medical Officer. Patients will be treated with the tisotumab vedotin dosing regimen followed by the patient in the base trial, until the investigator determines that the patient is no longer benefitting from treatment (i.e., disease progression or unacceptable toxicity has occurred), the trial is terminated by the sponsor, the patient withdraws consent, or for other reasons as defined in this protocol.

In the Treatment Phase, investigators will monitor and assess the patients for response to treatment and for disease progression. Timing and assessments are outlined in the Schedule of Activities (Table 1). Any SAEs, non-serious grade ≥ 2 ocular AEs, non-serious grade ≥ 3 AEs, overdose and/or medication errors, and pregnancies should be reported to the Safety CRO by trial site personnel within 24 hours of their knowledge of the event. All (S)AEs should be reported from the time the patient has signed the ICF until the End-of-Trial (EOT) Visit, or until the patient withdraws consent or starts subsequent anti-cancer therapy, whichever occurs first.

An EOT Visit will occur 30 days after the last administration of trial drug. However, if a patient is unable to return to the site at that time or if the patient is scheduled to start subsequent treatment, this visit should be performed as soon as possible after the last administration of trial drug.

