8.2 Schedule of Activities

Table 1: Trial Flow Chart - 1Q3W Treatment Scheme

Procedure	Screening (up to 21 days before Day 1)	Treatment Period Cycle 1 – X (21-day cycle \pm 7 days) Day 1	End-of-Trial Visit (30 days after last dose + 1 week)	Comments
Informed consent	X			
Eligibility criteria	X			
Demography	X			
Height	X			
Weight	X	X		To be taken at screening and at start of each treatment cycle
Pregnancy test	X	X		To be taken at screening and at start of each treatment cycle for women of childbearing potential
Vital signs	X	X		Blood pressure pulse, heart rate and temperature taken at screening and before and after treatment
ECG	X	X		To be taken at screening and before each treatment
ECOG performance status	X			
Neuropathy assessment	X			
Skin assessment	X			
Ophthalmology evaluation	X	X	X	To be performed according to the schedule in the base protocol. Patients experiencing ocular symptoms must be referred to an ophthalmologist for prompt review (preferably within 72 hours and no later than within 1 week).
Laboratory sampling	X	X	X	Local laboratories will be used. Screening laboratory samples do not need to be repeated if performed at the base trial. Details on laboratory samples are provided in Section 10.3.4.

Procedure	Screening (up to 21 days before Day 1)	Treatment Period Cycle 1 – X (21-day cycle \pm 7 days) Day 1	End-of-Trial Visit (30 days after last dose + 1 week)	Comments
Trial drug administration		X		Treatment administration schedule to follow the treatment schedule in the base protocol.
Preventive eye therapy		X		Preventive eye therapy to be administered in relation to infusions as detailed in Section 9.5.4.
Response assessment (CT-scan, PSA, CA 125)	X	X	X	Last CT-scan of base trial to be used at screening if less than 4 weeks old, otherwise a new CT-scan needs to be obtained. Then, to be performed every 6 weeks (at the end of every second cycle) during Treatment Period, and response to be confirmed 4 weeks later. Response assessments will be recorded in the eCRF. PSA will be performed for CRPC patients. CA 125 will be performed for patients with ovarian cancer.
Radionuclide bone scan		X		For patients with CRPC, assessment of bone metastases by radionuclide bone scan every 12 weeks is recommended, but frequency should be based on local standards. If there is suspicion of progression, another bone scan will be performed twelve weeks later.
AE/SAE review	X	X	X	
Concomitant medication	X	X	X	

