8.5.1 Inclusion Criteria

Patients **MUST** satisfy all of the following entry criteria before they will be allowed to participate in the trial:

1. Patients must have either:
 - a) completed the base trial and have shown a clinical benefit of SD or better and have never met any withdrawal criteria as defined in the tisotumab vedotin base protocol, or
 - b) not completed treatment as defined in the base protocol for reasons that are not considered critical and unmanageable for the safety of the patient (as evaluated by the investigator and/or the sponsor) and the patient clearly showed response of PR or better.

2. Patients must not have experienced radiographic disease progression or clinical signs of symptoms of instability requiring urgent intervention.
3. Patients must not have received any other anti-cancer treatment (including surgery, radiation or systemic chemotherapy) since the base trial.
4. Acceptable renal function defined as: Glomerular filtration rate (Cockcroft-Gault) > 45 mL/min.
5. Acceptable liver function defined as:
 - a) Alanine aminotransferase and aspartate aminotransferase ≤ 3 times the upper limit of normal (ULN); if liver tumor/metastases are present, then $\leq 5 \times$ ULN is allowed,
 - b) Bilirubin $\leq 1.5 \times$ ULN, except in patients diagnosed with Gilbert's syndrome, direct bilirubin $\leq 2 \times$ ULN.
6. Acceptable hematological status (hematologic support is allowed if administered at least one week before scheduled Cycle 1 Day 1) defined as:
 - a) Hemoglobin ≥ 5.6 mmol/L (~ 9 g/dL). An absolute value > 8 g/dL is allowed if stable (> 4 weeks) during the base trial.
 - b) Absolute neutrophil count $\geq 1500/\mu\text{L}$ ($1.5 \times 10^9/\text{L}$).
 - c) Platelet count $\geq 75 \times 10^9/\text{L}$.
7. Eastern Cooperative Oncology Group (ECOG) performance status of 0 or 1.
8. A negative serum pregnancy test (if female and aged between 18-55 years old).
9. Patients, both females and males, of reproductive potential must agree to use adequate contraception during and for six months after the last infusion of tisotumab vedotin.

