 - a) Adequate contraception for women is defined as hormonal birth control or an intrauterine device (safe hormonal contraceptives include contraceptive pills, implants, transdermal patches, hormonal vaginal devices or injections with prolonged release). In countries where two highly effective methods of contraception are required this will be an inclusion criterion (refer to [Appendix 2](#)).
 - b) Male patients must be willing to use a latex condom during any sexual contact with females of childbearing potential during and for six months after the last infusion of tisotumab vedotin, even after having undergone a successful vasectomy.
 - c) In order to be considered as sterilized or infertile, a patient must have undergone surgical sterilization (vasectomy/bilateral tubectomy; hysterectomy and bilateral ovariectomy) or be postmenopausal (12 months or more with no period prior to enrolment).

10. Following receipt of verbal and written information about the trial, patients must provide signed informed consent before any trial-related activity is carried out.
11. Acceptable coagulation status as defined in the applicable base protocol:
 - GEN701: Acceptable coagulation status: international normalized ratio (INR) ≤ 1.2 (without anticoagulant therapy) and activated partial thromboplastin time (aPTT) ≤ 1.25 ULN; patients on stable doses of therapeutic anti-coagulative treatment for ≥ 8 weeks (e.g., warfarin) must have an INR ≤ 3 .
 - GEN702: Acceptable coagulation status defined as: INR ≤ 1.2 (without anticoagulant therapy) and aPTT \leq ULN.

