11.4 Reporting of Adverse Events after Termination of Trial Participation

Any suspected IMP-related SAE, non-serious grade ≥ 2 ocular AEs and non-serious grade ≥ 3 AEs occurring at any time after the patient has terminated trial participation, should be emailed to the Safety CRO at [REDACTED] if there is access to a secured email, or if there is no access to a secured email, faxed to [REDACTED].

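### Pregnancy reporting ends with trial participation, about 30 to 37 days after the last dose, although the protocol requires contraception for six months after the last infusion

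*Protocol*

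**What the plan says.** **Reporting duty.** Protocol 11.3.3 opens with "Any pregnancy that occurs during trial participation must be reported". It then gives the 24-hour timeline and the form. It requires follow-up of the outcome, the mother and the child (the child to at least one month of age), and covers partners of male patients under a separate consent. Its last sentence keeps one duty alive after trial completion: an SAE associated with a pregnancy must be reported if the investigator considers it possibly related to the drug.

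**Adverse event (AE) window.** Protocol 11.2 states "Any event of pregnancy must be reported as an AE to the Safety CRO". The window in the same section is "All AEs must be reported from the time the patient signs the ICF until 30 days after the last dose of tisotumab vedotin", and it closes sooner on withdrawal of consent or start of another anti-cancer therapy.

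**End of participation.** Protocol 8.1 states "An EOT Visit will occur 30 days after the last administration of trial drug", with an earlier visit if the patient cannot return or is about to start other treatment. Table 1 in 8.2 gives the column as "End-of-Trial Visit (30 days after last dose + 1 week".

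**After participation.** Protocol 11.4 deals with events "occurring at any time after the patient has terminated trial participation". It names suspected drug-related SAEs, non-serious ocular AEs of grade 2 or higher, and non-serious AEs of grade 3 or higher. Pregnancy is not on the list.

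**Contraception.** Under inclusion criterion 9 (8.5.1), patients of either sex with reproductive potential "must agree to use adequate contraception during and for six months after the last infusion of tisotumab vedotin". For men, condom use applies "during and for six months after the last infusion of tisotumab vedotin, even after having undergone a successful vasectomy".

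**The concern.** The protocol itself marks the six months after the last infusion as a time when conception is to be avoided, in women and in partners of treated men. Its reporting rule covers roughly the first of those six months. A pregnancy is not in itself one of the seriousness criteria in 11.1.2, so the post-participation list in 11.4 does not pick it up.

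The outcome and child follow-up in 11.3.3 has nothing to start it without an initial report. If only related serious outcomes reach the sponsor, it holds adverse cases without the number of exposed pregnancies or the normal outcomes needed to interpret them. The primary objective is long-term safety data, so this information is within the trial's purpose.

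**Working it through.** The plan gives no figure of its own on this point, so the check is a comparison of time windows.

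**Inputs**
- Contraception after the last infusion: six months (8.5.1, criterion 9). The documents give no length in days; 180 to 184 days is assumed, with 182.6 as the average.
- Days from last dose to end of participation: 30 (8.1), or 37 with the one-week window (Table 1: 30 + 7).
- Equating the end of participation with the EOT Visit is a reading of 8.1 and 8.5.3.2; the protocol does not define the term. The AE window in 11.2 leads to the same 30 days.

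**Formula**

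Uncovered days = six months − days to end of participation. Uncovered share = uncovered days ÷ six months.

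| Six months taken as | EOT at day 30 | EOT at day 37 |
|---|---|---|
| 180 days | 150 days (83.3%) | 143 days (79.4%) |
| 182.6 days | 152.6 days (83.6%) | 145.6 days (79.7%) |
| 184 days | 154 days (83.7%) | 147 days (79.9%) |

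The range is 143 to 154 days, or 79% to 84%. An EOT Visit brought forward, as 8.1 allows, makes the share larger.

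**Does another section close the gap?**
- 11.2: no. Pregnancy is reported as an AE, and that window closes at 30 days or sooner.
- 11.4: no. Pregnancy is not listed.
- 11.3.1 and 11.5 (Table 3): no. They set timelines and forms, not a period.
- The 24-hour sentence in 11.3.3: it sets a timeline. Read after the opening sentence, it does not lengthen the period.
- The last sentence of 11.3.3: in part. It catches serious outcomes thought possibly related. Spontaneous abortion must be reported as an SAE (11.3.3) and a birth defect is a seriousness criterion (11.1.2), so both qualify if thought related.

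**What remains uncaptured:** a pregnancy conceived after participation ends that is uncomplicated, or whose outcome is judged unrelated or non-serious.

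**After the fix:** with reporting to six months after the last infusion, the uncovered part falls to 0 days.

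**The case against.** The strongest reply is that contraception and reporting are separate rules and nothing in the protocol says their durations must match. That stands: this is a design choice with a gap, not a contradiction between two instructions.

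A reader might also infer more than the text supports:
- *That all late pregnancies are lost.* They are not. The last sentence of 11.3.3 has no time limit and keeps possibly related serious outcomes reportable. Section 11.7 follows ongoing SAEs beyond participation.
- *That most of the whole contraception period is uncovered.* Criterion 9 also spans treatment, where reporting applies. As an illustration only, assume 12 months of treatment: about 5 of 18 months (28%) would be uncovered. The 79% to 84% belongs to the post-infusion six months alone, and it is a share of calendar days, not of pregnancies.
- *That a planned analysis is compromised.* The primary endpoint is adverse events, and endpoints are only listed (Protocol 12.2; SAP section 4). The SAP plans a pregnancy listing (11.8 and Listing 16.02.03.14) and no pregnancy-outcome estimate.
- *That patients are not told to call the site after leaving.* The consent form was not available for this review, so that cannot be judged.

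The expected size of about 25 patients also stands as a reason to expect few events, though the documents give no pregnancy rate. These points limit the weight of the concern. None of them supplies a duty to report an uncomplicated pregnancy conceived in, say, the third month after the last infusion.

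**Conclusion.** The concern holds in a limited form. Between the end of participation and six months after the last infusion, 143 to 154 days (79% to 84% of that post-infusion period) carry no duty to report a pregnancy as such. Pregnancies during treatment are covered, and possibly related serious outcomes remain reportable afterwards.

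The result rests on two assumptions: six months is 180 to 184 days, and participation ends at an EOT Visit on day 30 to 37. The documents do not support calling this a contradiction, a loss of all late pregnancies or a threat to any planned efficacy result. It is a modest, correctable gap in safety follow-up.

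**What to change.** 1. In 11.3.3, state the period: any pregnancy in a patient, or in a female partner of a male patient, from signature of the consent form until six months after the last infusion, in line with criterion 9. The start should stay at consent signature, where 11.2 places it now. A start at first dose would narrow present coverage, and it would be unclear whether the base trial or this trial was meant.
2. Add pregnancy to the list in 11.4, and cross-refer from 11.2 so that its 30-day limit and earlier stopping events do not cut the pregnancy period short.
3. At the EOT Visit, remind patients to notify the site of a pregnancy within that time.

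**Cost.** The wording is short, but it needs a protocol amendment with the approvals in 15.2, and an updated consent form with repeat consent if the change is judged to alter procedures. Each late report could bring partner consent, outcome follow-up and child follow-up to at least one month of age, after the patient has left the trial. With about 25 patients this should be little work. Notification is passive and uses the existing Pregnancy Form. No visit or test is added, and no contraception or treatment rule changes.
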